DA VINCI TRANSORAL ROBOTIC-ASSISTED SURGERY OF PITUITARY GLAND

ACRONYM: ROBOPHYSE

BIOMEDICAL RESEARCH RELATING TO A MEDICAL DEVICE

NCT 02743442

DCT-2015-043

IDRCB: 2015-A01597-42

February 01, 2019

Introduction

In recent years, pituitary surgery has been enriched with endoscopic techniques. However, the latter still have some problems: endonasal complications, tightness of the focus, limited instrument handling, 2D vision. Many surgical specialties have adopted the da Vinci system (urology, oto rhino laryngology, gynecology, etc.) to improve their interventions with the following advantages: 3D vision, instrument maneuverability, abolition of physiological tremor.

Hypotheses

Following our published cadaveric work (Chauvet *et al.*, Neurosurgical Review 2014), we propose a new minimally invasive technique of pituitary surgery, transoral, assisted by the da Vinci robot.

Primary Objective

To confirm the feasibility of a new minimally invasive technique of pituitary surgery, transoral, assisted by the da Vinci robot

Secondary Objectives

- To improve post-operative outcomes and comorbidities related to this surgery
- To improve average lengths of stay

Main Evaluation Criterion

Feasibility of tumor (pituitary adenomas) resection

Secondary Evaluation Criteria

- 1) Accessibility of the sella turcica
- 2) Occurrence of adverse events attributable to surgery
- 3) Duration of postoperative hospital stay

Methodology

This is a biomedical research on a group of patients with pituitary adenoma.

This work seeks to test a new robot surgical technique - already used in other surgical specialties - in neurosurgery for pituitary tumors.

The operative indications will be set according to the usual criteria and confirmed during collegial meetings in the Department of Neurosurgery of the Ophthalmological Foundation A. de Rothschild (Paris, France).

The surgical procedure will be performed in the operating room of the Otorhinolaryngology and Head and Neck Surgery Department of the European Hospital Georges Pompidou (Public Assistance of Paris Hospitals, France), which already uses the da Vinci robot. An intraoperative radiography system will be used during the guiding procedure. At any time during surgery, a conversion for a conventional endoscopic pathway will be feasible to overcome any technical problems related to the robot (never reported during cadaveric work).

The postoperative follow-up will be done in the Neurosurgery Department of the Ophthalmological Foundation A. de Rothschild (Paris) according to the standard protocols.

Inclusion Criteria

- 1) Pituitary adenoma with an indication for surgery: visual compression and chiasmatic syndrome, HTIC, hormonal syndrome (hypopituitarism and hypersecretion), failure of drug treatments for prolactinoma
- 2) Absence of pituitary apoplexy requiring emergency surgery;
- 3) Spontaneous mouth opening greater than 35 mm
- 4) Patient affiliated to a social security scheme (or benefiting from the "Couverture Médicale Universelle");
- 5) Patient having signed a prior, free and informed consent.

Non-inclusion Criteria

- 1) Insufficient mouth opening
- 2) Intercurrent pathology (such as infection) of the oropharyngeal sphere and cavum
- 3) Complicated forms of pituitary adenoma with invasive pituitary adenoma type
- 4) Haemostatic disorders (thrombocytopenia <75,000 platelets / mm³, TP <60%, INR > 1.5, ongoing antiplatelet or anticoagulant therapy)
- 5) Phlebitis or active pulmonary embolism
- 6) Patient under judicial protection
- 7) Pregnant or lactating woman

Statistical Analysis Plan

The statistical analyzes will be exclusively descriptive.

Continuous variables will be described using the usual position and dispersion statistics, namely mean, median, variance, minimum, maximum and quartiles. The modalities of the qualitative variables will be described using numbers and proportions.

Number of subjects needed: 8

Total duration of study: 31 months

Inclusion period: 24 months

Duration of participation for a patient: approximately 7 months

Number of participating centers: 1

Average number of inclusions per month per center: 1

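### Does the main criterion need to name the robotic route and say how conversions to endoscopy are counted?

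*Combined protocol and SAP*

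**What the plan says.** The Primary Objective is "To confirm the feasibility of a new minimally invasive technique of pituitary surgery, transoral, assisted by the da Vinci robot". The Main Evaluation Criterion is "Feasibility of tumor (pituitary adenomas) resection", with no route, no extent of removal and no success threshold. The first secondary criterion is accessibility of the sella turcica. Conversion is not listed as a criterion.

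The Methodology section states "This work seeks to test a new robot surgical technique" and then adds: "At any time during surgery, a conversion for a conventional endoscopic pathway will be feasible to overcome any technical problems related to the robot". It also notes that such problems were not seen in the cadaveric work.

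The Statistical Analysis Plan says "The statistical analyzes will be exclusively descriptive". For categorical data it says "The modalities of the qualitative variables will be described using numbers and proportions". It defines no analysis set or denominator. The sample size is given as "Number of subjects needed: 8", without a derivation.

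**The concern.** The objective concerns a technique, whereas the criterion, read literally, concerns an outcome that a different technique can also produce. A patient converted to endoscopy and then resected has had a tumour resection, so the criterion's words alone would let that patient count as feasible. With no analysis set defined, a converted or aborted case could also be left out of the denominator.

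Relative to a robot-only count over all patients, both departures can raise the rate or leave it unchanged, and neither can lower it. The ambiguity therefore favours the new technique. The plan has no hypothesis test, so the observed proportion is the whole primary result, and each of 8 patients carries 1/8 = 12.5 percentage points. Since conversion is not a listed criterion, a reader might not learn that one had occurred.

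**Working it through.** **The plan's own figure.** The only relevant number is 8. The documents give no expected rate, threshold, precision target, alpha or power, so it can be neither reproduced nor contradicted. The question of how to count conversions does not depend on it.

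**Notation.** Let c be the number of conversions among 8 patients, s the share of those later resected by endoscopy, and r the number resected without conversion. All three are assumptions. The illustration takes every non-converted case as resected, so r = 8 − c.

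- Robot-only, all patients: r/8
- Any route: (r + s·c)/8
- Converted cases left out: r/(8 − c)

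**Results with s = 1** (exact Clopper-Pearson 95% intervals):

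| Conversions | Robot-only | Any route | Left out |
|---|---|---|---|
| 1 | 7/8 = 87.5% (47.3 to 99.7) | 8/8 = 100% (63.1 to 100) | 7/7 = 100% (59.0 to 100) |
| 2 | 6/8 = 75.0% (34.9 to 96.8) | 8/8 = 100% (63.1 to 100) | 6/6 = 100% (54.1 to 100) |
| 3 | 5/8 = 62.5% (24.5 to 91.5) | 8/8 = 100% (63.1 to 100) | 5/5 = 100% (47.8 to 100) |

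**Sensitivity to the assumptions.**

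- With s = 0.5, the average any-route rate is (7 + 0.5)/8 = 93.75%, (6 + 1)/8 = 87.5% and (5 + 1.5)/8 = 81.25% for c = 1, 2 and 3.
- With s = 0, the any-route and robot-only rates are identical, and only the denominator question remains.
- With one conversion later resected and one non-converted case not resected (r = 6), the three counts are 6/8 = 75.0%, 7/8 = 87.5% and 6/7 = 85.7%.
- With c = 0 and no aborted case, all three counts agree.

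**How likely is a conversion?** For an assumed rate p, the chance of at least one conversion in 8 patients is 1 − (1 − p)^8: 33.7% at p = 0.05, 57.0% at 0.10 and 83.2% at 0.20. These are chances of a conversion. The robot-only and any-route counts differ only if a converted case is then resected.

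**Which count does the text support?**

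- *Any route.* The title, hypothesis, objective and Methodology all concern the robotic transoral technique. The Methodology describes conversion as a way out of technical problems with the robot. Scoring such a case as a success would contradict the objective that the criterion serves.
- *Left out.* Nothing provides for removing a patient: there is one group, one centre and no per-protocol or evaluable set. Because counts are reported with proportions, a shortened denominator would show as 7 instead of 8.
- *Robot-only, all patients.* This is the only count that needs no departure from the objective or from the stated group.

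**The case for a change.** The strongest case for a change is that the objective implies the numerator but writes no rule, and it is silent on the denominator. Someone who accepts robot-only counting could still report 7/7 instead of 7/8. A conversion scored as a success would not be visible in the counts, because 8/8 looks the same either way. Eight patients could be described one by one, but nothing requires it. The cadaveric experience gives no clinical conversion rate, and the plan itself provides for conversion. Closing the gap would take a few sentences.

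Most of the facts in this stand. The rule is absent, and a hidden conversion in the numerator would not show. Accessibility of the sella gives only partial cover: a conversion caused by failed access might appear there, but that criterion is undefined too.

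What does not stand is the step from silence to a wrong result. The plan states no rule that miscounts anyone. To reach 100%, an analyst would have to credit the robot with the work of the conventional method, or drop a patient without any provision for it. The low cost of clearer wording does not make its absence an error.

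Parts of the proposed remedy are also open to debate. The only reason for conversion that the Methodology mentions is a technical problem with the robot. Counting every conversion as a failure, whatever the reason, is one defensible choice; separating robot-related from other reasons is another. The extent of removal that counts as resection is a separate missing definition.

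**Conclusion.** No change to the plan follows. This is missing detail that an analyst would fill sensibly from the objective: a case completed by endoscopy is not evidence that the robotic route is feasible, and all patients in the group stay in the denominator. Describing any conversion and its reason would be ordinary reporting in a series of 8.

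The possible effect on the reported figure is 12.5 points per converted-then-resected patient. That size rests entirely on assumed conversion counts, assumed resection after conversion, and the assumption that the remaining patients are all resected. Even then no conclusion is tipped, because the plan has no test, threshold or go/no-go rule. It is certain that the documents contain no counting rule; it is much less certain that this would mislead anyone.

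### The only specified adverse-event result is limited to events attributed to surgery, a judgement that readers of an uncontrolled 8-patient series cannot check; show all recorded events beside it

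*Combined protocol and SAP*

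**What the plan says.** The Secondary Evaluation Criteria section lists three items, and the second is "Occurrence of adverse events attributable to surgery". No other listed criterion names adverse events. The main criterion is whether resection is feasible, and the other two secondary criteria are access to the sella and length of the postoperative stay. The matching aim, first under Secondary Objectives, is "To improve post-operative outcomes and comorbidities related to this surgery".

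On design, the Methodology section states: "This is a biomedical research on a group of patients with pituitary adenoma". It describes no comparator group.

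Inclusion criterion 1 gives the indications for surgery, among them "visual compression and chiasmatic syndrome, HTIC, hormonal syndrome (hypopituitarism and hypersecretion". The Non-inclusion Criteria remove some patients with other possible causes of later events, for example "Complicated forms of pituitary adenoma with invasive pituitary adenoma type", clotting disorders and oropharyngeal infection. They do not remove patients with visual or hormonal deficits.

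The Statistical Analysis Plan is purely descriptive and sets 8 subjects. For categorical data it says: "The modalities of the qualitative variables will be described using numbers and proportions". Postoperative follow-up is "according to the standard protocols", and each patient takes part for about 7 months.

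The document does not say who decides attribution, by what rule or over what period. It specifies no table or listing of all recorded adverse events.

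**The concern.** An attribution filter is safest where background events can be recognised, either against a comparator or because patients start without the problems in question. Neither holds here. A patient operated on for visual compression whose vision is worse afterwards may have been harmed by the procedure or may have progressing disease. The same applies to a new or deeper hormonal deficit. Someone has to decide, and a reader given only the attributed events cannot see which events were set aside.

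The error can run either way. An event that surgery caused but that is judged unrelated disappears from the specified result. An event with another cause that is judged related stays in the count, and its misclassification is not visible.

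What is at stake is the readability of the only adverse-event result planned for a new technique that, in this document, rests on cadaveric work. With 8 patients, one such judgement can decide whether the summary reads as no complication or as one patient in eight.

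**Working it through.** **Inputs.** The planned number of patients is N = 8 (Statistical Analysis Plan). The plan gives no formula, precision target or event rate behind that figure, so it cannot be reproduced; it is not in dispute here. The documents give no rate of adverse events and no rate of misjudged attribution, and none is assumed below. Two working assumptions are made: the robotic procedure is started in all 8 patients, and criterion 2 is summarised as the number of patients with at least one qualifying event.

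**Notation.**
- m = patients with at least one recorded adverse event of any cause (unknown)
- a = patients with at least one recorded event judged attributable (the specified result is a/8)
- t = patients with at least one recorded event that surgery truly caused (unknown)

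**Step 1: range that attribution alone leaves open.** Every patient counted in a is also counted in m, so 0 ≤ a ≤ m and the specified result lies between 0/8 and m/8.

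| m | Lowest a/8 | Highest a/8 |
|---|---|---|
| 1 | 0/8 = 0% | 1/8 = 12.5% |
| 2 | 0/8 = 0% | 2/8 = 25.0% |
| 3 | 0/8 = 0% | 3/8 = 37.5% |

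These are logical limits. They treat each judgement as free to fall either way and do not describe what is likely.

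**Step 2: direction.** The error in the specified result is (a − t)/8. Since 0 ≤ a ≤ m, it lies between −t/8 and (m − t)/8. For example, with m = 2 and t = 1 it runs from −1/8 = −12.5 points to (2 − 1)/8 = +12.5 points. The sign is not fixed.

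**Step 3: weight of one judgement.** If one patient's only counted event is reclassified, the result moves by 1/8 − 0/8 = 12.5 points. If that patient has another counted event, it moves by 0. The step of 1/8 applies to any yes/no criterion in 8 patients. It shows what one misjudgement can do and says nothing about how often one occurs.

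**Step 4: what the all-event count adds.** Every patient counted in t is also counted in m, so t ≤ m. The figure m/8 is therefore a ceiling on the proportion of patients with a recorded surgery-caused event, and it does not depend on anyone's attribution. It does not estimate procedural harm, because it includes events due to disease or other causes.

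**The case against.** **The criterion fits its objective.** Secondary objective 1 concerns outcomes and comorbidities linked to the operation, and a count of surgery-attributed events answers that question. This stands, which is why the attributed count should be kept. An all-event count answers a different question and is useful only as a check beside it.

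**The document is very short.** Its analysis section names no table for any criterion, and the general sentence on categorical variables neither promises nor excludes an all-event table. This also stands. A reader might infer that events judged unrelated go unrecorded, but the documents do not say so. The point is confined to what the specified result contains.

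**Any attribution-limited criterion leaves out events judged unrelated.** This is true by definition, and nothing in the documents shows that misjudgement is likely here. A reader might infer that the result will understate harm. That is not supported, because the error can go in either direction and its net effect cannot be derived. The ground for the point is narrower: no comparator, deficits present before surgery, and no stated attribution rule.

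**Conversion to another route.** The Methodology section allows that "a conversion for a conventional endoscopic pathway will be feasible". A reader might infer that events in converted cases would escape the count. They would not, because criterion 2 refers to surgery, not to the robot, and an event from either route remains a surgical event. Conversion can blur which route caused an event, but it is no support for this point.

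**Nothing depends on the count.** No test, threshold or stopping rule is tied to it. This stands and limits the priority.

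**The fix does not define attribution.** This is also correct. Showing both counts makes the judgement visible but does not supply the missing assessor, rule or time window.

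**Conclusion.** The point holds as a reporting weakness of modest weight. The plan's only specified adverse-event result is filtered by a judgement that its readers cannot check, in an uncontrolled series whose patients may already have the kinds of deficit that would need to be attributed.

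For size, only an illustration is available: one reclassified patient out of 8 is 12.5 points, provided all 8 are operated on as planned and that patient has no other counted event. No probability or direction of error can be given from the documents. Reading the 12.5 points as an expected bias would go beyond them.

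The primary feasibility result and the sample size of 8 are unaffected. The change is a cheap improvement of optional to moderate priority.

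**What to change.** Reword secondary criterion 2 along these lines: *All adverse events recorded during participation from the start of the procedure, in all patients in whom the robotic procedure was started (including converted cases), with those judged attributable to surgery shown beside them.*

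For each of the two categories, give the number and proportion of patients with at least one event. Add a short de-identified listing that shows, for each event, the attribution made and the deficits the patient had before surgery. All of this fits a purely descriptive plan.

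**Cost.** The change needs one rewording, one small table and a listing for about 8 patients. Because it is limited to events already recorded, it asks for no new data collection.

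**Downsides.**
- The event table becomes slightly longer and includes disease-related and unrelated events, so the all-event count must be read as a ceiling beside the attributed count.
- If standard follow-up does not record every event, the all-event count is incomplete to that extent, and the report should say so. If only attributed events are recorded, the second column adds nothing.
- A listing of about 8 patients having a new operation at named hospitals needs care against re-identification.

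### Does an average of 1 inclusion per month, set against 8 subjects in 24 months at one center, call for a change to the plan?

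*Combined protocol and SAP*

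**What the plan says.** The figures are consecutive lines at the end of the Statistical Analysis Plan section of the combined protocol and SAP:

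- size: "Number of subjects needed: 8"
- recruitment window: "Inclusion period: 24 months"
- follow-up: "Duration of participation for a patient: approximately 7 months"
- overall length: "Total duration of study: 31 months"
- sites: "Number of participating centers: 1"
- recruitment rate: "Average number of inclusions per month per center: 1"

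The same section limits the analysis to summaries: "The statistical analyzes will be exclusively descriptive". The document gives no derivation of the 8. It also gives no ratio of screened to included patients, no dropout or replacement allowance, and no staggered start or planned pause that would link the rate to the other figures.

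**The concern.** Rate, number of centers and length of recruitment normally multiply to the number of patients. Here they do not, and the gap is a factor of three. Because the plan has no sample-size calculation, these lines are its only quantitative planning content, so a conflict among them attracts attention.

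Two things could be at stake. The intended number of patients might not be 8. Or the sponsor might have no usable benchmark for recruitment: one patient every three months would be on schedule under one reading and at a third of schedule under the other. In a trial with a power calculation, an accrual-driven interim look or a rule for stopping slow recruitment, either would matter.

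**Working it through.** **Inputs**, all from the closing lines of the Statistical Analysis Plan section: N = 8 subjects; c = 1 center; r = 1 inclusion per month per center; T = 24 months of inclusion; F = about 7 months of participation; total = 31 months.

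**1. The total duration reproduces.** T + F = 24 + 7 = 31 months, as stated. This shows that the durations agree with one another. It does not independently confirm the 24, since the 31 is evidently built from it.

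**2. The number of subjects does not reproduce from the rate.** r × c × T = 1 × 1 × 24 = 24, against 8 stated: a difference of 16 and a ratio of 3.

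**3. Each figure implied by the others.**

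| Held fixed | Implied figure |
|---|---|
| N = 8, T = 24 | rate = 8 / 24 = 0.33 per month, one patient every 3 months |
| N = 8, r = 1 | inclusion = 8 / 1 = 8 months; total = 8 + 7 = 15 months |
| r = 1, T = 24 | N = 24 |

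The 15-month total is derived here; the document gives only 31.

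**4. Can rounding explain the printed 1?**

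- To the nearest whole number: no. 0.33 rounds to 0. The slowest rate that rounds to 1 is 0.5 per month, which gives 0.5 × 24 = 12 patients in the window, or fills 8 places in 8 / 0.5 = 16 months (total 16 + 7 = 23, still 31 − 23 = 8 months short).
- Up to the next whole patient: yes, 0.33 becomes 1. The figure would then no longer be a true average, and the document does not say it was rounded up.

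**5. Can loss of patients explain it?** Going from 24 included to 8 evaluable would need a loss of (24 − 8) / 24 = 67%. The document mentions no such loss.

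**6. Does anything depend on the answer?** At 0.33 per month, 8 patients take the full 24 months. At 1 per month they take 8, leaving 24 − 8 = 16 months unused. Recruitment fits the window in both cases. The planned outputs are means, medians, variances, ranges, quartiles, counts and proportions for the 8 patients, and none has the rate as an input. The one duration among the endpoints, postoperative hospital stay, is measured within each patient and does not depend on how fast patients arrive.

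**The case for a change.** The strongest case for a correction is that the mismatch is certain, can be checked by hand, and would cost a few words to remove. An average describes the whole recruitment period, so its natural meaning is that it holds over all 24 months. The document does not call the 24 months a maximum, and a recruitment window three times as long as needed would be unusual. If the true expectation is 0.33 per month, the window has no slack, and a reader who takes the printed rate at face value would expect recruitment to finish far too early.

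Most of this stands as a description of the text: the line is unreconciled, and the document does not show which figure is wrong. What does not stand is that a reader is left without a study duration. Inclusion period, participation and total are each stated and agree; only the expected pace is unclear. Nor do the figures strictly exclude each other, since a window that stays open longer than the minimum needed is slack rather than contradiction. The product of 24 is not evidence that 24 patients were intended, because the number of subjects is stated outright as 8. The loss of a recruitment benchmark is real but has no consequence here: the primary objective is whether the robot-assisted surgery can be done, not how fast patients can be recruited, and no decision is tied to pace.

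**Conclusion.** The mismatch is real and no change to the plan follows. Its size is a factor of three in the stated pace (1 against 0.33 per month), confined to one administrative line. The most economical readings are a rate rounded up to a whole patient or a 24-month outer limit; either reconciles the figures, although the document confirms neither.

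Correcting the line would alter no endpoint, analysis, number of patients or decision. The conclusion rests on three features of the plan: a purely descriptive analysis, a stated size of 8 that is not derived from the rate, and the absence of any interim look or accrual-based rule. If any of these were otherwise, the line would need to be reconciled before use. As the plan stands, an analyst would summarize the 8 patients in the same way under every reading.
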